In addition, the conversation manager also manages the “state” of the conversation—including the flow of interactive conversation (e.g., the flow of the above-mentioned steps), and adaptive responses based on user input. The conversational state is adaptively managed based on user input. Towards this end, user “intents” or statements are parsed and mapped into pre-defined categories, which are then mapped to the appropriate state in the PST interaction to deliver relevant content, aligned with the user input. The conversation manager also provides dynamic support for functions such as resume, which allows participants to re-start a previously incomplete PST session. Such stop-restart functions provide flexibility in conversational interactions, affording perceptions of realistic conversational interactions.

The conversation manager also interacts with a **context manager** module that provides situated and contextual information regarding Lumen sessions. The context manager primarily controls three aspects: persistence of therapy content across sessions, scheduling/re-scheduling of sessions, and integrating external content (e.g., surveys, EMAs) into the Lumen sessions. The context manager dynamically tracks user problems (see step 1 above), and potential action plans that were previously developed and evaluates adherence to those plans in ensuing sessions. Such dynamic follow-up increases the persistence and continuity of therapy across sessions, developing trust and confidence in the virtual coach. Similarly, the context manager tracks session progress (e.g., session 5), and helps participants schedule and re-schedule sessions. With its integration with an external scheduling database (in REDCap), follow-up emails and messages are tracked to ensure that the therapy sessions are synchronized with participant needs. Finally, the context manager also interacts with the REDCap database to incorporate survey responses (e.g., completion of the PHQ-9 and GAD-7 surveys) into the Lumen session. For example, prior to the start of each Lumen session, participants are asked to complete the PHQ-9 and GAD-7 surveys; if incomplete (or partially complete), Coach Lumen reminds the user to complete the survey prior to re-starting the session. Further, if a user delays session attendance after having completed the surveys, Lumen checks whether a survey is current (within 3 days) to

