#### ***B.3.c. Dosing analyses***

Dosing analyses will be conducted **within the Lumen treatment group**. The primary dosing analysis will examine the relationship of neural target activation in the amygdala and DLPFC to the 4 measures of dose (number and length of PST sessions, fidelity-weighted number and length of PST sessions). The secondary dosing analysis will examine the relationship of PROs, ecological end-of-day assessments, and measures of treatment progress (e.g., PHQ9 and GAD7 across PST sessions) to the same 4 measures of

dose. Note that given neural target activation measures and PROs are obtained at weeks 0 and 16, these analyses will focus on change over the full 16-week span of the study, whereas ecological end-of-day assessments and treatment progress measures are available for a total of 8 occasions each, and thus will be considered longitudinally.

**Neural targets:** The primary dosing analyses will consist in the separate regressions of change in activation from week 0 to 16 for the amygdala and DLPFC on each dose variable. This results in 8 separate regressions: amygdala on number of sessions, amygdala on length of sessions, amygdala on fidelity-weighted number, amygdala on fidelity-weighted length, and also DLPFC on the same 4 dose variables. Assumptions of linear regression will be verified and corrected through data transformation as needed. Our purpose is to identify variants of the dose variables with the strongest association (i.e., highest  $R^2$ ) with change over 16 weeks in the 2 neural targets. If the coefficient for dose in these regressions is positive and significant, it confirms that the dose variable is associated with higher change in neural target activation.

**Patient-reported outcomes:** Depression and anxiety symptoms, functioning, and health-related quality of life will be measured at week 0 and 16. Thus, the secondary dose analysis for PROs mirrors the primary analysis for neural targets. That is, change from week 0 to 16 in the PROs will be separately regressed on the 4 dose variants, resulting in separate PRO-dose measure regressions. As in the primary analysis, our purpose is to identify variants of the dose variables with the strongest association (i.e., highest  $R^2$ ) with change over 16 weeks in the PROs of interest.

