**Treatment progress measures:** To monitor treatment progress, symptoms (PHQ9, GAD7) and treatment acceptability (usability, user experience, and treatment alliance) will be measured in each PST session at weeks 1, 2, 3, 4, 6, 8, 10, and 12 (for a total of 8 occasions). Similar to the analyses of ecological measures as described above, we will implement polynomial and logarithmic models and compare model

fit using BIC. These regressions'  $R^2$ 's will allow us to examine in detail the relationship of treatment progress and cumulative dose, with fidelity-to-PST taken into account using the fidelity-weighted number and length of PST sessions. Additionally, as is common in psychotherapy in general, it is possible that not all participants will complete the full 8 sessions as some may drop out early owing to either lack of improvement or “enough” improvement based on self-assessment or yet other reasons related or unrelated to the treatment. Using the Good-Enough-Level (GEL) model, some studies of in-person psychotherapy showed that the rate of change varied as a function of treatment duration, namely, the rate of change (progress) was faster for patients attending fewer sessions but slower for those attending more sessions. In other words, patients may remain in treatment until they improve. To explore whether a similar pattern is present for Lumen PST, we will apply the GEL modeling approach by extending the polynomial models for treatment progress measures, in particular, PHQ9 and GAD7, to include a fixed effect of total treatment dose (e.g., total number of sessions) and interactions between total treatment dose and linear, quadratic, and cubic rates of change. Essentially, the GEL model is a stratified analysis that examines dose effects across strata of participants with similar treatment dose (e.g., similar number of sessions attended), as opposed to aggregate dose effects across all participants. Furthermore, we will conduct exploratory analyses of baseline characteristics in relation to the dose effects on neural targets, PROs, ecological measures, and treatment progress measures. We anticipate that baseline characteristics (e.g., severity at presentation, sex as a biological variable, sociodemographics) may be related to dosing estimates (e.g., via actual sessions completed). To explore these relationships, baseline characteristics and their interactions with dose measures will be added to the models as described above.

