#### **B.4. Intention to Treat (ITT) and Handling Missing Data**

Clinical trials such as the one proposed must face the issues of dropout and missing data. We have put in place a strong plan to ensure maximum retention of participants through the course of the study, with a projected 85% or greater retention (see the *Recruitment and Retention Plan*). Data missing completely at random (MCAR) may be analyzed “as is” without imputation, as it does not introduce bias into estimates and inferences. More commonly, data are missing at random (MAR) owing to covariate-dependent events (e.g., irregular work shifts, children’s illness, transportation, and scheduling foul-ups). Our primary analysis technique, linear mixed models, is robust for MAR and provides unbiased estimates of model parameters without imputation. (One may impute as well, but the benefit is usually modestly improved power rather than changes to conclusions.) The more serious concern for behavioral interventions is the possibility that data will be missing not at random (MNAR). This occurs when dropout or missingness is related to the level of the outcome of interest (e.g., a participant’s level of depression or anxiety). If treatment is working well and symptoms of depression and anxiety have lessened, then participants may feel continuation in treatment is not necessary or beneficial. They drop out or miss sessions because the treatment seems to have worked. On the other hand, if participants experience no improvement in symptoms, they may drop out or miss sessions because they are discouraged that the treatment seems not to have worked. In either case, the loss of data is related to the outcomes under study and has the potential to bias the study’s conclusion about the intervention. Handling the problem of MNAR is difficult. First, there is no test for the presence of MNAR (*vs.* MAR). Second, there are many possible underlying sources of MNAR and there is no guarantee that explorations of missing data patterns will clearly reveal those sources. Third, missing data imputation for MNAR necessarily makes strong and untestable statistical assumptions, so that conclusions from imputed MNAR datasets must remain tentative. This picture reinforces our strong commitment to participant retention (see the Study 1 *Recruitment and Retention Plan*).

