Missing data imputation implemented via SAS procedures MI, MIANALYZE, and MCMC will be carried out to reexamine all primary and secondary analysis. This effectively implements ITT as traditionally conducted. Specifically, both missing outcomes and covariates will be imputed under the

assumption that data are MAR. The fully conditional specification (FCS) approach allows each variable type to be imputed with an appropriate model: linear, discriminant, logistic, or Poisson regression. The algorithm for FCS is implemented in procedure MI: 100 imputed data sets will be created, each imputation is analyzed using MIXED, and finally MIANALYZE combines 100 sets into final estimates. This approach to MAR has been widely adopted given its robust performance. Because linear mixed models estimated via direct likelihood as in MIXED offer unbiased estimates under MAR, the benefit of multiple imputation lies in compliance with the ITT fill-in requirement and modestly increased power. We anticipate these results to differ little from those provided by the primary analysis.

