#### ***B.4.a. Sensitivity of results to missing data assumptions***

These will be conducted by varying the models used for imputation. There is no test for NMAR, but we will examine missing data frequency by condition and in covariate subgroups to detect and diagnose differential dropout. If warranted, we can shift to a Bayesian joint modeling approach to imputation using MCMC. The mathematical statistical underpinnings of sensitivity analysis for missing data imputation have advanced substantially (see, for example, the treatment of selection models in Chapter 8 of Daniels and Hogan). However, the software implementation of these techniques has lagged behind the theory. Simpler approaches have been implemented in SAS at this time; however, the more complex techniques involving semiparametric specification of the Daniels and Hogan extrapolation model are not readily available. During the data collection years, this problem will likely be resolved. Here, we mention 3 approaches that seem feasible now: (1) With just a few data collection waves, the number of frequently occurring missing data patterns is likely 3 to 6 for neural targets and PROs and 8 to 10 for ecological assessments and treatment progress measures (some infrequent patterns can be grouped together); these patterns can be used to specify a pattern mixture model for the missing data. Such models merely include an indicator variable for each pattern and thereby provide a straightforward means to adjust results for missing data. If results are not much altered by inclusion of pattern indicators, then concern about missing data assumptions is diminished; (2) Mallinckrodt et al. reviewed simulation and other studies of the impact of MNAR on trial results (primary analyses like those we plan) and concluded that the impact of violations is rarely substantial. The R statistical environments add-on package ‘mice’ now has capabilities to create particular violations of MAR and MNAR assumptions, so that simulation-based exploration of violations using our own data will now be possible; and (3) SAS PROC MI has now incorporated an option to use a SCALE parameter (suggested range between 1.5 and 2.0) to explore the sensitivity of results to imputations relying on the MAR assumptions.

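### The imputation and pattern-indicator rules in B.4 and B.4.a cover session-based progress scores with no exception for PST sessions that were never held, so they cannot serve as missing-data checks on the number-of-sessions dose models

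*Combined protocol and SAP*

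**What the plan says.** Appendix 3, B.3.c says of the progress measures (PHQ9, GAD7, usability, user experience, alliance) that they "will be measured in each PST session at weeks 1, 2, 3, 4, 6, 8, 10, and 12". Appendix 2 lists NASA-TLX, UEQ-S and WAI-Tech as end-of-session surveys. Under Appendix 1, Section A, "prior to the start of each Lumen session, participants are asked to complete the PHQ-9 and GAD-7 surveys". B.3.c expects that "not all participants will complete the full 8 sessions as some may drop out early".

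The dose models for these measures are secondary: "The secondary dosing analysis will examine the relationship of PROs, ecological end-of-day assessments, and measures of treatment progress" to the four dose measures. The dose variables are cumulative to date, the models carry linear, quadratic and cubic time terms, and the GEL extension is to "include a fixed effect of total treatment dose (e.g., total number of sessions") and its interactions with the rates of change.

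B.4 discusses missed sessions as lost data; of participants who improve it says "They drop out or miss sessions because the treatment seems to have worked". It then states: "Missing data imputation implemented via SAS procedures MI, MIANALYZE, and MCMC will be carried out to reexamine all primary and secondary analysis". Missing outcomes and covariates are imputed under MAR by fully conditional specification, in 100 data sets. B.4.a expects 3 to 6 missing-data patterns for neural targets and PROs and "8 to 10 for ecological assessments and treatment progress measures". It proposes one indicator per pattern and treats concern as reduced if the results hardly move. Neither section says what to do with a session that was not held.

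**The concern.** A week-16 scan or PRO that was not obtained is an ordinary missing value: it was due for every randomized participant regardless of attendance. A progress score is tied to a session, and sessions run in order. When a participant stops, the later scores are absent because the later doses were not given. Absence and dose are then nearly the same information, while B.4 treats absence as a separate nuisance to be filled in or adjusted for.

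At stake is how the secondary dose results for PHQ9, GAD7 and the session surveys are read. B.4 presents the imputed re-analysis as the ITT version and expects it to differ little from the main analysis. B.3.b says that assessing dose in several ways will show which measure to use in Study 2. A re-analysis that gives a slope near zero by construction, or a check that cannot be computed for one term, could mislead that reading.

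**Working it through.** **Inputs.** From the documents: 40 Lumen participants; 8 sessions at weeks 1, 2, 3, 4, 6, 8, 10 and 12, hence 40 × 8 = 320 possible session records; acceptability limits of at least 95% with 1 or more sessions and at least 80% with 4 or more (Section 3.0); 8 to 10 patterns (B.4.a). The documents give no SD, within-person correlation, stopping rate for sessions 5 to 8, or imputation model. Those are assumptions below.

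**Step 1: the plan's pattern count.** With sequential sessions, stopping after session 1, 2, …, 8 gives 8 patterns, or 9 with zero sessions. Both lie in the stated 8 to 10. The anticipated patterns therefore correspond to the number of sessions completed.

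**Step 2: how many records could be affected.** Suppose attendance just meets the limits: 38 of 40 with at least one session and 32 of 40 with at least four.

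- Fewest sessions: 2×0 + 6×1 + 32×4 = 134, leaving 320 − 134 = 186 (58%) not held.
- Most sessions: 2×0 + 6×3 + 32×8 = 274, leaving 320 − 274 = 46 (14%) not held.

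The 58% end requires everyone to stop at the minimum and is a bound, not a forecast.

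**Step 3: session surveys.** An end-of-session rating of workload or alliance has no value where there was no session. No missingness assumption gives an imputed value a meaning.

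**Step 4: PHQ9 and GAD7 in the number-of-sessions model.** In held-session rows with sequential sessions, everyone at occasion k has the same cumulative number. The columns intercept, occasion and cumulative number have rank 2 of 3. With time entered as a cubic in weeks, R² of session number on time is 0.999. Held sessions thus carry almost no information on dose at a given time. Imputed rows do supply a contrast: dose is frozen at the last session while the imputed score follows those who kept attending.

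Simulation of the slope per session, with cubic time and a random intercept. Assumptions: n = 40, SD 4, within-person correlation 0.7, stopping unrelated to scores, level unchanged after stopping, no time effect, about 15% of rows imputed, imputation from earlier scores without dose.

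| True slope | Imputed analysis: slope | Imputed analysis: SE | Held sessions only: SE |
|---|---|---|---|
| −0.5 | about 0.00 | about 0.35 | about 1.65 |
| −0.25 | about 0.00 | about 0.35 | about 1.65 |
| 0 | about 0.00 | about 0.35 | about 1.65 |

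The 95% half-width falls from 1.96 × 1.65 = 3.23 to 1.96 × 0.35 = 0.69 points per session, with the centre at zero in every row.

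A second simulation (within-person SD 2, 35% stopping at random after 2 to 7 sessions, dose adjusted for occasion, again no dose in the imputation) agrees:

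| Truth | Slope on complete scores | Slope after imputation | Imputed change, last score to week 12 |
|---|---|---|---|
| −0.8 per session | −0.81 | 0.00 | −2.8 |
| −0.4 per session | −0.41 | 0.00 | −1.4 |
| −0.5 per week, no dose effect | −0.01 | 0.00 | −3.2 |
| no change | −0.01 | 0.00 | about 0 |

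In the first two rows, stoppers are credited with improvement at no added dose.

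**Step 5: pattern indicators in the GEL model.** Intercept, three time terms, total sessions and its three interactions with time make 8 columns, rank 8. Adding 7 pattern indicators gives 15 columns, rank 14. The lost dimension is the main effect of total sessions, which is a function of the pattern. The three interactions remain estimable. Cumulative number is not collinear with the indicators (rank 9 of 9). Total session length is only partly explained by them (R² about 0.73 if length per session has a log-SD of 0.3, an assumption).

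**The case against.** A reader might go further in four ways. The documents do not support these readings.

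- **That PHQ9 and GAD7 are undefined after the last session.** They describe symptoms that continue, and Appendix 1 foresees a survey completed before a delayed session. Such scores can properly be called missing. The fault lies in imputing them under MAR without dose and then using them in a dose model.
- **That imputation hides a dose effect the plan would otherwise find.** On held sessions alone, the time-adjusted slope with true value −0.5 has an SE near 1.7 and is significant in about 6% of runs. Imputation replaces an uninformative estimate with one that looks informative. Without time terms the slope barely moves (−0.80 observed, −0.84 imputed). If time alone drives improvement, the imputed slope of about 0 is correct.
- **That the pattern indicators are the dose.** They determine total number of sessions only, not cumulative, length-based or fidelity-weighted dose. B.4.a lists the pattern model as one of three feasible approaches, allows rare patterns to be grouped, and does not name the GEL model, which is itself exploratory.
- **That the dose work as a whole fails.** Direct likelihood is the main analysis. The primary dosing analysis uses week 0 to 16 neural targets, so the choice of a dose measure for Study 2 does not rest on progress measures alone.

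It is also fair that the imputation model is unstated and might include dose. That may not repair matters: cumulative number is constant among observed rows at each occasion, and a simulation adding total sessions to the imputation gave a slope of +0.06 against −0.51 on complete scores. Session dates that drift from schedule would loosen the identity somewhat.

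What remains is a stated rule with no exception, applied to measures for which it cannot do its job.

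**Conclusion.** The point holds in a limited form. Three items are affected:

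1. Imputed end-of-session ratings for sessions not held have no meaning. This needs no numerical assumption.
2. The imputed PHQ9 or GAD7 slope per session, adjusted for time, goes to about 0 with an SE of about 0.35 instead of about 1.65. This rests on sequential sessions close to schedule, an imputation model without dose, and the assumed SD, correlation and stopping. The ±0.69 interval would still include a true −0.5; the fault is that its centre and width reflect the imputation, not the data.
3. For the GEL main effect of total number of sessions, the pattern check cannot be read if a full set of indicators is used. Grouping patterns loosens this.

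The GEL interactions, the length and fidelity-weighted doses, the direct-likelihood analyses, the week 0 to 16 dose regressions and Criteria 1 and 2 are not affected. The consequence is confined to secondary re-analyses in the Lumen arm, but the correction is cheap and worth making before analysis.

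**What to change.** In Appendix 3, B.4:

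- Limit imputation of treatment progress measures to scores lost at sessions that were held.
- State that NASA-TLX, UEQ-S and WAI-Tech are not imputed for sessions not held.
- State that PHQ9 and GAD7 are not imputed after a participant's last session for the dose models.
- Say plainly that the number-of-sessions slope adjusted for occasion is close to unidentified from held sessions, so that neither a null nor a wide interval is over-read.

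In B.4.a, do not use session-pattern indicators as the missing-data check for models that contain total number of sessions.

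The cost is a few sentences of SAP text and somewhat less computing. The downside is small: the progress-measure dose models lose their imputation supplement. The change does not recover a time-adjusted dose effect from held sessions; it removes a re-analysis that would appear to settle the question.

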#### ***B.4.a. Sensitivity of results to missing data assumptions***

These will be conducted by varying the models used for imputation. There is no test for NMAR, but we will examine missing data frequency by condition and in covariate subgroups to detect and diagnose differential dropout. If warranted, we can shift to a Bayesian joint modeling approach to imputation using MCMC. The mathematical statistical underpinnings of sensitivity analysis for missing data imputation have advanced substantially (see, for example, the treatment of selection models in Chapter 8 of Daniels and Hogan). However, the software implementation of these techniques has lagged behind the theory. Simpler approaches have been implemented in SAS at this time; however, the more complex techniques involving semiparametric specification of the Daniels and Hogan extrapolation model are not readily available. During the data collection years, this problem will likely be resolved. Here, we mention 3 approaches that seem feasible now: (1) With just a few data collection waves, the number of frequently occurring missing data patterns is likely 3 to 6 for neural targets and PROs and 8 to 10 for ecological assessments and treatment progress measures (some infrequent patterns can be grouped together); these patterns can be used to specify a pattern mixture model for the missing data. Such models merely include an indicator variable for each pattern and thereby provide a straightforward means to adjust results for missing data. If results are not much altered by inclusion of pattern indicators, then concern about missing data assumptions is diminished; (2) Mallinckrodt et al. reviewed simulation and other studies of the impact of MNAR on trial results (primary analyses like those we plan) and concluded that the impact of violations is rarely substantial. The R statistical environments add-on package ‘mice’ now has capabilities to create particular violations of MAR and MNAR assumptions, so that simulation-based exploration of violations using our own data will now be possible; and (3) SAS PROC MI has now incorporated an option to use a SCALE parameter (suggested range between 1.5 and 2.0) to explore the sensitivity of results to imputations relying on the MAR assumptions.

